2. STUDY DESIGN

Please refer to the study protocol for a full description of the trial design. This is a single-blind, pragmatic three-arm, parallel group, randomised trial. Participants will be recruited nationwide, using multi-media advertising with targeted promotion to reach Māori, Pacific and low socio-economic groups given their disproportionately higher smoking prevalence.

Potential participants interested in the trial will register on a trial website. Participants will be asked for on-line consent to complete an online screening questionnaire to determine their eligibility for the trial and verify their phone number. Eligible and interested participants will then provide online consent to enter the trial.

A copy of the consent form and participant information sheet will be automatically emailed by the online system to the participant for their records. Participants will also be asked to provide online consent to inform their general practitioner that they are participating in the trial. Via the online platform the baseline data will be collected, and then participants will immediately be randomised to either 12 weeks of: 1) cytisine plus nicotine e-cigarette, 2) cytisine; or 3) nicotine e-cigarette.

All 12-weeks of trial products will be couriered to participants immediately after randomisation. The courier company will notify the study centre immediately after the courier pack has been delivered, which will trigger the scheduling of the 'quit date' follow-up call and the start of the text-based behavioural support programme. Participants will be asked to begin their treatment the day after they receive their courier pack and to reduce their smoking *ad libitum* over the first four days of treatment so that they are not smoking at all by the fifth day ('quit date').

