Participants will be called on their quit date to verify they are quitting on that day (and to collect outcome data). If a participant states that they are not quitting on the scheduled 'quit date', they will be given one chance to reset their quit date within the next seven days, with this date becoming their new 'quit date' (which will trigger the scheduling of all subsequent follow-up calls). For participants who are unable to be contacted at quit date, their 'quit date' will be set in the system as six days after they received their courier pack (which will trigger the scheduling of all subsequent follow-up calls). Participants will be advised to continue with their allocated treatment irrespective of any lapses back to smoking.

Outcome assessments will be undertaken at one, three, and six months after the Quit date, and at 12 months in a subsample. At the six-month follow-up, in-person carbon monoxide tests will be performed for participants who live in the Auckland region to verify self-reported continuous smoking abstinence.

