All participants will receive the text-based behavioural support STOMP programme (developed and tested by the National Institute of Health Innovation, University of Auckland). This text message programme provides personalised smoking cessation advice, support, and motivation to support individuals to quit smoking and maintain cessation. The programme includes messages covering information relevant to quitting, tips to cope with cravings, advice on avoiding smoking triggers, and motivational support. The programme includes 2-way functionality to support individuals during cravings and is personally tailored. Regular, personalised text messages providing smoking cessation advice, support, and distraction will be delivered over a six-month period (five messages a day for six weeks, then three per week until the end of the 26th week – i.e., six-month follow-up).

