2.4. Sample size

A sample size of 800 (N=300 in the cytosine group, N=300 in the cytosine plus nicotine e-cigarette group, and N=200 in the nicotine e-cigarette group) will provide 90% power at two-sided $p=0.05$ to detect an absolute difference of 13% in six-month smoking abstinence rates between the combination treatment group and the cytosine group, and 16% difference between the combination treatment group and the nicotine e-cigarette group (taking account of multiple testing).

The predicted difference is based on trial evidence for six month verified continuous abstinence quit rates of 9% for nicotine e-cigarettes, 12% for cytosine, and 25% for combination cessation treatment (averaged). The sample size accounts for a 28% loss-to-follow-up at six months.

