4. STUDY OUTCOMES

4.1. Primary outcome

Verified six-month continuous abstinence (using Russell Standard) defined as self-report of smoking not more than five cigarettes from the Quit date and confirmed by an expired air carbon-monoxide (CO) measurement with a Bedfont Smokerlyzer (≤ 9 ppm signifying abstinence). Biochemical validation of self-reported cessation for Auckland participants will involve a researcher visiting participants within 72 hours if they claim to be abstinent, to obtain a CO reading. For participants outside of Auckland who self-report that they are smokefree, verbal consent will be sought from them to provide their contact details to their region's community-based smoking cessation service, so that they can undertake the CO monitoring within 72 hours. Sensitivity analysis will be undertaken looking at different cut-offs for the CO measurement, given lack of consensus about the best reading to use

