- **Adverse events and serious adverse events**: self-reported adverse events are collected at each follow-up call, with adverse events coded using MedDRA. In addition, participants can at any time report an adverse event via a web-based adverse event diary.

- **Change from baseline in weight and body mass index** (three and six months)
- **Change from baseline in general health** (three, six and 12 months): shortness of breath, cough, asthma, chronic pain, COPD, and mental health. Measured for participants who answered Yes to the general health question at baseline, and is measured using a five-point scale (much worse, a bit worse, about the same, a bit better, much better).
- **Concomitant medication:** other medications taken during the course of the study
- **Cost outcomes:** cost-per- quitter, cost-per-person reducing their daily cigarette consumption, and the incremental cost-effectiveness ratio
- **Text-based behavioral support STOMP program received:** total number received up until end of the six month follow-up or they opt out of receiving the messages.

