7.5. Primary outcome analysis

The proportion of participants that have been biochemically verified as continuously abstinent at six months by group will be analysed using log-binomial regression, and the risk in each group, relative risks, absolute risk differences, and corresponding 95% confidence intervals will be calculated. All analyses for the

primary outcome will be ITT (unless otherwise stated) and include all randomised participants. Missing outcomes will be imputed using multiple imputation assuming the data is missing at random. Multiple imputed datasets will be created (n=50) and the imputation model will include baseline age, sex, and group, and the fully conditional specification logistic regression method will be used to impute the missing outcomes. The imputed datasets will be analysed using log-binomial regression and combined to output one inference. Adjusted analyses for potential covariates will be conducted if needed.

To check the robustness of the primary outcome the following sensitivity analyses will be conducted:

- self-reported continuous abstinence at 6 months (not biochemically verified)
- using the following varying cut-offs used for CO measurements: ≤ 3 ppm, ≤ 5 ppm, ≤ 8 ppm

The following sensitivity analyses will also be conducted for the primary outcome where groups will be compared using chi-squared tests:

- complete case analysis
- per protocol analyses where participants that have any major protocol violations will be excluded (see 6.2)
- assuming all missing outcomes are still smoking instead of using multiple imputation

Tests for heterogeneity will be used to examine if there is any difference in the groups on the unadjusted primary outcome for the following subgroups: baseline age (will be dichotomised based on the median), sex, ethnicity (Māori, non-Māori), education (< 12 years of attending school, 12 or more years of attending school), type of cigarettes smoked (RYO, factory made, both), AUDIT-C (low, high), cannabis use, motivation to quit, level of cigarette dependence (using HSI), and level of behavioural support received (will be categorised based on the data). Subgroup analyses will also be conducted by batch number of product received (Batch 1: early 2022, Batch 2: early 2023) to assess if there were any differences by batch.

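### The subgroup test by level of text support received uses a factor that builds up after randomisation, mostly while the primary outcome is being decided

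*SAP*

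**What the plan says.** SAP section 7.5 plans tests for heterogeneity of the unadjusted primary outcome over a single list: age, sex, ethnicity, education, cigarette type, AUDIT-C, cannabis use, motivation, dependence (HSI), and finally "level of behavioural support received (will be categorised based on the data". The other factors in that list are baseline data; batch number is handled in a separate sentence. No measure, number of categories or cut-point is given for support level, and no caveat is attached.

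The SAP's only measure of support received is a secondary outcome in section 4.2: "total number received up until end of the six month follow-up or they opt out of receiving the messages". Section 2.2 gives the schedule as "five messages a day for six weeks, then three per week until the end of the 26th week". Section 2 has products couriered after randomisation, with confirmed delivery triggering the quit-date call "and the start of the text-based behavioural support programme". The primary outcome in section 4.1 rests on "self-report of smoking not more than five cigarettes from the Quit date", with CO confirmation at six months.

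**The concern.** A subgroup test supports a statement about effect modification when the strata are fixed before treatment can act on them. Randomisation then holds within each stratum. Here all arms are offered the same programme, so the amount received can differ only through what happens after randomisation. The SAP names one such event, opting out.

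A participant who relapses and then stops the texts lands in the low-support stratum because of the outcome. If opting out also differs by arm, the arms within a stratum are no longer comparable. The result could then be reported as the combination working better or worse with more text support, when the pattern comes only from how the strata were formed. Choosing the categories after seeing the data adds a further degree of freedom.

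**Working it through.** **Which measure is meant.** Section 7.5 does not say. I take it to be the message count in section 4.2, the only measure of support received in the SAP. The timing argument does not depend on this choice, because any measure of support received from this programme accrues after randomisation.

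**Timing.** Scheduled messages only:

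- First six weeks: 5 × 42 = 210. Weeks 7 to 26: 3 × 20 = 60. Total 270.
- Treatment starts the day after delivery and the quit date is its fifth day. If texts start on the delivery day, 5 days × 5 = 25 messages precede the quit date (25/270 = 9.3%).
- Participants not reached on the quit date have it set at six days after delivery: 6 × 5 = 30 (11.1%).
- Participants not ready to quit: "they will be given one chance to reset their quit date within the next seven days". That gives at most 12 × 5 = 60 (22.2%).

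So 78-91% of scheduled messages fall after the quit date.

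**Expected stratum results.** Let p be the abstinence rate in an arm, a the proportion of abstainers who stay in the text programme (high support) and b the proportion of relapsers who do. Then

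- risk in high support = p·a / [p·a + (1−p)·b]
- risk in low support = p(1−a) / [p(1−a) + (1−p)(1−b)]

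The planning rates in section 2.4 are 25% (combination) and 12% (cytisine), a true RR of 2.08 and RD of 13 points. The values of a and b are assumptions. Texts have no effect on quitting in any scenario. With b = 0.6 in both arms and a = 0.9 in the combination arm:

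| a in cytisine arm | High support: risks, RR | Low support: risks, RR |
|---|---|---|
| 0.90 | 33.3% vs 17.0%, 1.96 | 7.7% vs 3.3%, 2.33 |
| 0.85 | 33.3% vs 16.2%, 2.06 | 7.7% vs 4.9%, 1.58 |
| 0.80 | 33.3% vs 15.4%, 2.17 | 7.7% vs 6.4%, 1.21 |

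In the first row the RDs are 16.4 and 4.4 points.

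These values assume complete outcome data. Section 2.4 states "The sample size accounts for a 28% loss-to-follow-up at six months", and in section 7.5 "the imputation model will include baseline age, sex, and group" but not support level. If 28% of outcomes in each stratum are drawn at the arm's overall rate, the stratum risk becomes 0.72 × (risk above) + 0.28 × p. For low support in the first row this is 0.72 × 7.7% + 0.28 × 25% = 12.5%, against 0.72 × 3.3% + 0.28 × 12% = 5.7%. The low-support RRs become 2.19, 1.83 and 1.58, and the high-support RRs 1.99, 2.06 and 2.15.

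**False rejection.** Simulated trials, 300 vs 300, Wald test of high against low support at two-sided 5%, 0.5 added to each cell. Full data and complete cases use 200,000 trials. Imputation uses 20,000 trials with 50 imputations from group only (age and sex taken as unrelated to outcome), pooled by Rubin's rules. Loss is 28%, independent of outcome and support. Entries are % rejecting on the RR / RD scale; paired values are combination vs cytisine.

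| Retention | Full data | Complete cases | Imputed |
|---|---|---|---|
| a = b = 0.7, both arms | 4.3 / 4.9 | 4.1 / 5.0 | 0.6 / 0.8 |
| a = 0.9, b = 0.6, both arms | 1.7 / 59.7 | 1.2 / 46.3 | 0.0 / 15.5 |
| a 0.9 vs 0.85, b = 0.6 | 6.5 / 73.6 | 5.1 / 59.2 | 0.3 / 25.4 |
| a 0.9 vs 0.8, b = 0.6 | 18.9 / 84.2 | 13.6 / 70.6 | 1.6 / 35.9 |
| a 0.9 vs 0.7, b = 0.6 | 57.6 / 95.8 | 43.4 / 87.4 | 13.4 / 61.7 |
| a 0.7 vs 0.9, b = 0.6 | 61.7 / 14.7 | 38.8 / 11.5 | 5.4 / 2.5 |
| b 0.5 vs 0.7, a = 0.9 | 16.5 / 97.2 | 13.2 / 90.6 | 1.7 / 63.6 |

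The RR column matches the log-binomial model. Part of the RD figure is a scale effect: baseline risk differs between strata, so a near-constant RR gives unequal RDs.

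**The case against.** The strongest reply is that the analysis as specified is unlikely to mislead. Section 7.5 models the primary outcome by log-binomial regression with imputation of missing outcomes. On that route, among the scenarios run for combination against cytisine, RR rejection exceeds 5% only with a 20-point difference between arms in the retention of abstainers. Nothing in the SAP points to so large a gap. The complete-data stratum RRs overstate the shift under imputation, and no RD interaction test is named. The SAP does not say that opting out follows relapse. Baseline age is also split on observed data, and motivation has no stated categories. One could argue that the word received already tells the reader this is a post-randomisation factor.

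Much of this stands as a limit on size: the RR-scale risk of a false positive is small unless the arms differ clearly. It does not answer the point of principle. The imputed test is quiet partly because its model omits support level and so pulls the strata together; even with retention unrelated to outcome it rejects in only 0.6%. That is no evidence that the strata are valid. The low-support RR still moves from 2.08 to between 1.58 and 2.19 after imputation. Age is measured before randomisation and has a set rule, the median; this item has neither property. A definition in the protocol could settle the measure, but it could not move receipt of messages to before randomisation.

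**Conclusion.** The concern holds. Section 7.5 treats a post-randomisation quantity as one more baseline subgroup, and 78-91% of its scheduled accrual overlaps the period in which the outcome is decided. A heterogeneity result by this factor cannot be read as effect modification by text support, whether or not the test rejects.

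The timing share follows from the SAP's schedule, assuming texts start on the day of delivery. The size of any distortion rests on assumed retention rates and on opting out being related to relapse; the SAP gives no figures for either. The harm is confined to this one subgroup result and how it is reported. The change is worth making, but the main conclusion of the trial does not depend on it.

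**What to change.** Take level of behavioural support received out of the heterogeneity tests in section 7.5. Report messages received, and the number and timing of opt-outs, descriptively by arm; the count is already a secondary outcome in section 4.2.

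If the sponsor wants to keep a comparison by support level, the SAP should state which measure is used, place it apart from the baseline subgroups, label it exploratory and non-randomised, and fix its categories before data lock.

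The cost is a change of SAP wording and, if the item is removed, the loss of one exploratory test.

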7.6. Secondary outcomes analysis

Descriptive summary statistics for each follow-up visit and group will be presented for all secondary outcomes. For all secondary outcomes (unless otherwise stated) participants with missing outcome data will be excluded from the analyses.

Incidence rates, risk difference, relative risks and 95% confidence intervals will be calculated for self-reported continuous abstinence (not biochemically verified), seven-day point prevalence abstinence and reduced CPD consumption by at least 50% outcomes at each follow-up visit. Both complete case analysis and ITT analysis (where missing outcomes will be imputed using the same multiple imputation method described above for the primary outcome) will be conducted.

MPSS at 3 months (for 6-month continuous abstainers only) will be analysed using linear regression and include baseline MPSS in the model. The change from baseline in each of the repeated continuous outcomes (average number of cigarettes smoked each day for smokers, weight and BMI) will be analysed using mixed models. Each model will include group and the baseline measure. The appropriate covariance structure to be used will be assessed by the likelihood ratio test. The method of maximum likelihood will be employed to ensure patients with missing data are included in the model assuming the data is missing at random. However, if all follow-up data is missing then the participant will be excluded from the analyses. Intervention by visit interaction effects will be tested. Note the

distribution of these continuous outcomes will be first assessed for normality and skewed data will be subjected to an appropriate transformation before analysis. Non-parametric analysis (Mann-Whitney tests) will be used for the continuous outcomes if data is skewed and cannot be transformed to be normally distributed.

The time to first lapse and relapse outcomes will be analysed using Kaplan-Meier curves, the log rank test, and Cox proportional hazards regression analysis.

If the primary outcome is significant then cost analyses will be conducted. The cost per quitter, cost per person reducing their daily cigarette consumption and incremental cost-effectiveness ratio will be compared with New Zealand data from Quitline and other NRT service providers, and international studies, and will take a health sector perspective. However, the tobacco expenditure savings to individual smokers will also be calculated (for those who quit and cut down) to give a more societal perspective on the benefits. This calculation will use data on the daily amount smoked prior to quitting and the price of the particular products smoked. For those who cut down their consumption by a significant margin (i.e., 25% or more), the cost per person reducing their daily cigarette consumption will be calculated.

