- **Alcohol use:** Measured using the Alcohol Use Disorders Identification Test (AUDIT-C). The AUDIT-C score is calculated by summing all three items and has range 0 to 12 where higher scores indicate greater risk of alcohol dependence. Note participants that tick 'Never' for the first AUDIT-C item (How often do you drink alcohol in the past year) then skip the next two AUDIT-C items, so for these AUDIT-C score to be set to value 0. For men, an AUDIT-C score ≥ 4 indicates an increased risk of hazardous drinking or alcohol dependence, while in women it is a score of ≥ 3 . And an AUDIT-C score ≥ 8 indicates a very high risk for both men and women.
- **Health related quality of life:** measured using the NZ EQ-5D
- **Signs and symptoms of nicotine withdrawal and urge to smoke:** measured using the Mood and Physical Symptoms Scale (MPSS) which consists of the following:
 - 5-point ratings of depressed mood, irritability, restlessness, hunger and difficulty concentrating. MPSS score is calculated by summing all 5 items and has a range of 5 to 25 where higher scores indicate greater nicotine withdrawal.
 - 6-point ratings of time spent with urges to smoke and strength of urges to smoke. Note the strength of urges question has values 1 to 5. Participants who tick 'Not at all' for time spent with urges to smoke have to then skip to the next section of questions and don't answer the question on strength of urges. So for these participants need to set strength of urges to equal value 0. [Therefore, this question will then have values 0 to 5]. The urge score is calculated by summing the two urges questions and has a range 0 to 10 where higher scores indicate greater urge to smoke.
- **Cannabis use:** Participants will be asked if they have used cannabis for recreational or non-medical purposes in the last 12 months.

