Participants that withdraw will be censored on the last available visit, and participants that have not relapsed by the six (or 12) month follow-up will be censored on the six (or 12) months visit date. Note the first follow-up form with a relapse date will be taken since this will be more accurately remembered by participants than later visits.

- **Use of other medication and other methods of cessation** (participants will be asked about their use of other methods of cessation, such as NRT, Zyban, clonidine, nortriptyline, e-cigarettes, acupuncture etc)
- **Health-related quality of life** (three, six and 12 months) measured using the New Zealand EQ-5D
- **Treatment use and compliance** (quit date, one and three months): use of the allocated product. This will include daily use (and reasons for not using daily), and number of pills or pods remaining.

For participants allocated to cytisine, compliance is defined as having taken $\geq 80\%$ of the required number of tablets over the three-month intervention period.

- **Signs and symptoms of nicotine withdrawal, and urge to smoke** (three months): measured using the MPSS
- **Crossover** where participants in the cytisine-only group will be asked whether they accessed and used an e-cigarette (with or without nicotine) during the six (or 12) month study period, and participants in the e-cigarette group will be asked whether they accessed and used cytisine during the trial.
- **Change in e-cigarette use**: Participants allocated to the e-cigarette groups will be asked whether they changed the type of e-cigarette device and/or the nicotine strength and/or flavor they used in the e-cigarettes provided. If they did, they will be asked when they did this, and what the device type, nicotine strength and/or flavor was.
- **Dual use** (not collected at quit date): defined as daily use of both their allocated treatment and continued smoking of cigarettes every day.
- **Continuation of product use** (at six and 12 months in a subsample) defined as continued use of their allocated treatment after the end of the designed three-month treatment period.
- **Acceptability of the product** (three months): Participants will be asked for their views on the use of their allocated product as a cessation aid
- **Recommendations** (three months): Participants will be asked whether they would recommend their allocated treatment to another smoker who wanted to quit.

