7. STATISTICAL ANALYSIS

All statistical analyses will be performed using SAS version 9.4 and R version 3.4.2. Data collected in the NIHI Redcap database will be extracted into SAS for the analyses. All statistical tests will be two-tailed and a 5% significance level throughout the analyses. No adjustments for multiplicity are planned for any of the outcomes.

Summaries of continuous variables which are normally distributed will be presented as means and standard deviations or medians and inter-quartiles for skewed data, while categorical variables will be presented as frequencies and percentages. Continuous variables will be compared with t-tests or Mann-Whitney tests and categorical data with chi-squared tests as appropriate.

A separate EXCEL file containing the SAP tables specific to this study will be provided based on all the analyses stated below (see Appendix I).

All regression analyses will be conducted for the following two comparisons:

- Cytisine plus nicotine e-cigarette group vs Cytisine only group
- Cytisine plus nicotine e-cigarette group vs Nicotine e-cigarette only group

Exploratory analyses will also be conducted comparing the Cytisine only and Nicotine e-cigarette only groups for the primary outcome.

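### EQ-5D has a baseline value and repeated follow-up but no named model, so any group comparison falls to an unadjusted test that is valid but less precise than the model used for weight and BMI

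*SAP*

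**What the plan says.** - **Collection.** SAP section 3 lists health-related quality of life at baseline, "measured using the NZ EQ-5D". Section 4.2 makes it a secondary outcome: "three, six and 12 months) measured using the New Zealand EQ-5D". Section 2 adds that the last follow-up takes place "at 12 months in a subsample".
- **Adjusted models.** Section 7.6 says that "each of the repeated continuous outcomes (average number of cigarettes smoked each day for smokers, weight and BMI) will be analysed using mixed models", and of those models that "Each model will include group and the baseline measure". They are fitted by maximum likelihood so that participants with some missing visits stay in. MPSS at three months has a separate rule: it "will be analysed using linear regression and include baseline MPSS in the model".
- **General rules.** Section 7.6 opens with: "Descriptive summary statistics for each follow-up visit and group will be presented for all secondary outcomes". Its default is to leave out participants whose outcome is missing. Section 7 says: "Continuous variables will be compared with t-tests or Mann-Whitney tests and categorical data with chi-squared tests as appropriate".
- **EQ-5D in section 7.** Neither EQ-5D nor quality of life is mentioned there, including in the cost paragraph of 7.6.

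**The concern.** EQ-5D has the features for which section 7.6 uses a baseline-adjusted repeated-measures model: a baseline value and more than one follow-up. Weight and BMI, followed up at three and six months, get that model. EQ-5D, followed up at three, six and 12 months, does not, and no reason is given.

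Two things are lost if the groups are then compared under the general rule. First, the baseline value is not used, so the interval is wider than it need be and any chance baseline difference stays in the estimate. Second, a participant seen at three months but not at six adds nothing to the six-month comparison, whereas a likelihood model would use the three-month value. Section 2.4 allows for 28% loss at six months, so this is not a remote case. A quality-of-life result showing no clear difference would be harder to interpret than the collected data allow.

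**Working it through.** **Step 1. Which rules reach EQ-5D?**

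| SAP rule | Reaches EQ-5D? | Uses baseline? |
|---|---|---|
| 7.6, descriptive summaries | Yes | No comparison made |
| 7.6, exclusion of missing outcomes | Yes | Not applicable |
| 7.6, mixed models | No: cigarettes per day, weight and BMI only | Yes |
| 7.6, linear regression | No: MPSS only | Yes |
| 7.6, Mann-Whitney if skewed | No: refers to the outcomes already listed | No |
| 7, t-test, Mann-Whitney or chi-squared | Yes, if a comparison is made | No |

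The parenthesis in the mixed-model sentence names three outcomes and does not present them as examples. The separate table file (Appendix I) is described in section 7 as built from the analyses stated in the SAP, so it should not add a model that the SAP lacks.

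**Step 2. What does ignoring baseline cost?** The SAP gives no figure for EQ-5D, so there is none to reproduce. For a continuous score at a single visit, with rho the correlation between baseline and follow-up:

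- variance of the adjusted group difference ÷ variance of the unadjusted one = 1 − rho²
- detectable difference at 80% power, two-sided 0.05, in SD units: unadjusted = (1.960 + 0.842) × √(1/n₁ + 1/n₂); adjusted = that × √(1 − rho²)

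Inputs:
- Randomised numbers are 300, 300 and 200, with 28% loss (section 2.4). Analysed: 300 × 0.72 = 216 and 200 × 0.72 = 144. It is an assumption that EQ-5D is lost at the rate planned for the primary outcome.
- rho is not in the SAP. Values of 0.3, 0.5 and 0.7 are assumed.

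Unadjusted:
- combination v cytisine: 2.802 × √(1/216 + 1/216) = 2.802 × 0.0962 = 0.27 SD
- combination v e-cigarette: 2.802 × √(1/216 + 1/144) = 2.802 × 0.1076 = 0.30 SD

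Adjusted:

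| Assumed rho | 1 − rho² | 216 v 216 | 216 v 144 |
|---|---|---|---|
| 0.3 | 0.91 | 0.26 SD | 0.29 SD |
| 0.5 | 0.75 | 0.23 SD | 0.26 SD |
| 0.7 | 0.51 | 0.19 SD | 0.22 SD |

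Put another way, the unadjusted comparison does as well as an adjusted one with 9%, 25% or 49% fewer participants.

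**Step 3. What the arithmetic leaves out.** It is for one visit. The further gain from using partial follow-up in a repeated-measures model is not sized here. It also applies only to a continuous score, not to EQ-5D dimension levels.

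**The case against.** The strongest reply is that section 7.6 selects some outcomes for formal models and leaves the rest descriptive. Several other secondary outcomes, such as crossover, dual use and acceptability, have no named model either. On that reading EQ-5D is never tested and no precision is lost. This stands as a possible reading, and a reader who infers that the SAP prescribes a t-test for EQ-5D at each visit goes further than the text: the section 7 sentence is general and leaves the choice of test to judgement. But the SAP nowhere says that EQ-5D is descriptive only, and that same sentence says continuous variables will be compared. Even on this reading, a model already specified for similar outcomes could be extended to EQ-5D at little cost.

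Other points that stand:
- The score is not named. If dimension levels are meant, the comparison would be chi-squared, also unadjusted, and the variance formula does not apply.
- The size of the gain rests on an assumed correlation. At 0.3 it is small.
- Adding EQ-5D to the list does not by itself secure the gain, because section 7.6 sends untransformable skewed outcomes to Mann-Whitney, which ignores baseline.
- A missing visit removes a participant from that visit's comparison only. It would be wrong to infer that one missed visit removes the participant from the EQ-5D analysis altogether.

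A reader might also infer that the urge-to-smoke score is left out in the same way. The text does not establish this: section 3 presents the MPSS as made up of both the five ratings and the urge ratings, so the three-month MPSS regression may cover both. The doubt arises only because section 3 defines the MPSS score itself from the five ratings.

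**Conclusion.** The point holds as a matter of efficiency. EQ-5D is a named secondary outcome with a baseline value, section 7 gives it no model, and the only comparison rule that reaches it ignores that baseline and drops missing values. For a continuous score at one visit, adjustment would reduce the variance by 9% to 49% across assumed correlations of 0.3 to 0.7. The difference detectable in the combination v cytisine comparison would fall from 0.27 SD to between 0.26 and 0.19 SD.

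It is tempting to call the fallback comparison biased or invalid because of chance baseline differences. The SAP does not support that: allocation is randomised, and the unadjusted interval already allows for chance imbalance. What is lost is precision and the use of partial follow-up. Neither the primary outcome nor the cost outputs described in section 7.6 depend on EQ-5D. The change is nonetheless worth making before data-lock, since the SAP already has both the data and the method.

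**What to change.** Amend section 7.6 as follows:

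1. Name the EQ-5D score to be analysed: the index, and the VAS if it is collected.
2. Add it to the mixed-model list with baseline EQ-5D as covariate and three and six months as visits. Include 12 months for the subsample only, treated as missing by design for everyone else, and state how the subsample was chosen so that this treatment can be judged.
3. If the score is too skewed to transform, use a method that keeps the baseline value, for example the same model with bootstrap intervals or an ordinal model with baseline as covariate, rather than an unadjusted Mann-Whitney test.
4. Confirm that MPSS in section 7.6 covers both the five-item score and the urge score, each with its own baseline value.

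If EQ-5D is in fact meant to be descriptive only, the SAP should say so. The cost is a few sentences and reuse of the code for weight and BMI. No new data are needed.
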